9.3 Data management

Data management will be performed according to SynteractHCR SOPs.

10. Statistical methods and determination of sample size

10.1 Statistical and analysis plan

A separate Statistical Analysis Plan (SAP) will be finalized that details the planned statistical analysis and may include necessary adaptations to the planned statistical analysis before unblinding of the data.

Any deviations from the planned analyses will be described and justified in the final integrated trial report.

10.1.1 General considerations

All data obtained in this trial and documented in the eCRFs will be listed and summarized with statistics or frequency tables as appropriate. In case of termination of the trial, all data collected up to that time point will be included into the analysis.

Raw data listings and summary tables will be generated using the software SAS[®] Version 9 or higher.

All statistical analysis will be descriptive i.e. no formal testing will be performed.

Continuous variables will be summarized with means, standard deviations, medians, minimums, and maximums and valid cases.

Other summaries (e.g. quartiles, 95% confidence intervals) may be used as appropriate. Categorical efficacy and safety variables will be summarized by counts and by percentage of patients in corresponding categories.

10.1.2 Classification of patients to subsets

For the statistical analysis the randomized patients will be divided up into the following datasets:

The following definitions are applicable:

Safety analysis set (SAS)	all patients who were randomized and received at least one dose of trial medication
Full analysis set (FAS)	all patients of the SAS with at least one measurement of the ADA titer at baseline
Per Protocol set (PPS)	all patients of the FAS for whom no relevant protocol deviations were documented

The analysis of the primary endpoint will be based on the FAS. A secondary analysis of the primary endpoint will be based on the PPS. Safety analysis will be based on the SAS.

The decision whether a protocol deviation is relevant or not for the exclusion of patients from the PPS set will be made case-by-case in a data review meeting.

10.1.3 Immunogenicity data

All immunogenicity parameters will be analyzed descriptively per treatment group. No statistical tests are planned. Baseline ADA-positive patients will be calculated as a percentage of the total number of patients whose baseline samples were tested for ADA. Titer will be reported as median and interquartile range.

95% confidence intervals for incidence rates and for rate differences will be given.

Secondary immunogenicity parameters will be described with appropriate descriptive statistics for dichotomous, categorical or continuous variables.

specific for GlucaGen and dasiglucagon, respectively, and the performance of the assays are thus not directly comparable. As a consequence, a formal comparison or non-inferiority analysis will not be performed

Currently, no ADA incidences have been detected in the completed clinical trials, where up to 5 repeated doses of dasiglucagon have been administered to the same patients within a week. Across the two phase 1 clinical trials and a completed phase 2 PK/PD trial, a total of 141 subjects have been exposed to dasiglucagon and no incidences of ADA development have been observed. The obtained data indicate that dasiglucagon has a low risk for induction of ADAs in the investigated settings and as a consequence a meaningful sample size to compare both treatments cannot be estimated.

The sample size is therefore based on a certain precision of the confidence interval for the overall ADA incidence if no events are observed, respectively to ensure a certain probability for observing one event.

When no events are observed, to obtain an upper bound of 0.050 on the 90.0% confidence interval for the probability of such a rare event, would require a sample size of 45. Respectively, accepting a chance of observing at least one event of 90% and an actual probability of the event of 5% leads to a sample size of 45 patients completing the trial. In order to account for drop-outs, it is expected that 112 patients in total will be randomized and treated.

11. Ethics and regulations

11.1 Independent ethics committees and competent authorities

The clinical trial authorization (CTA) granted by the competent authority (CA) and a favorable opinion from the relevant independent ethics committee(s) (IEC(s)) /Institutional Review Board (IRB) will be obtained prior to the start of the trial. The local authorities will be notified about the trial as required by law.

The CA and the EC/IRB will be notified about the end of the trial and a report summarizing the trial results will be sent to the CA and the EC within one year after the end of the trial. If the trial is terminated early, the CA and the EC will be notified within 15 days.

The IECs and/or IRBs met the requirements of the International Conference on Harmonisation (ICH) Harmonised Tripartite Guideline for Good Clinical Practice (GCP) and local legislation. They also met the requirements of 21 CFR 312.3.

11.2 Ethical conduct of the trial

The trial will be conducted in accordance with the ethical principles set forth in the Declaration of Helsinki (including amendments).

11.3 Patient information and consent

Written informed consent will be obtained from all patients prior to entry into the trial. The investigator will explain to each patient orally and in writing (patient information sheet) the nature, significance, risks and implications of the trial before inclusion. In particular, the patients will be informed about the following:

- the possibility of withdrawing from the clinical trial at any time by revoking the consent and without any resulting disadvantage
- how personal and health-related data will be collected and used during the trial
- the patient must be informed that his/ her medical records may be examined by authorized monitors or Clinical Quality Assurance auditors appointed by the Sponsor, by appropriate IEC members, and by inspectors from regulatory authorities.

All patients will receive a copy of the patient information sheet and a copy of their signed and dated informed consent form.

All patients will be insured against injury caused by their participation in the trial according to legal requirements. They will be informed about the insurance and the resulting obligations on their part.

11.4 Legal and regulatory requirements

This trial will be carried out in accordance with:

- ICH guidelines for GCP, United States investigational new drug (IND) regulations (21 CFR 312), the regulations on electronic records and electronic signature (21 CFR 11), the most recent guidelines of the Declaration of Helsinki, and the relevant laws and regulations of the country in which the trial takes place.
- Standard operating procedures (SOPs for clinical investigation and documentation in force at SynteractHCR)

12. Trial administration

12.1 Responsibilities

Zealand A/S is the sponsor of this trial. SynteractHCR, a contract research organization (CRO), will organize the performance of this trial.

A list with the names and addresses of the responsible institutions and persons is provided in Appendix 1 of this protocol.

12.2 Protocol deviations

The investigator agrees to conduct the trial in compliance with the protocol. Prospective protocol deviations or waivers will not be granted for this trial.

Any deviation from the clinical trial protocol in the conduct of the clinical trial will be notified to the Monitor on an ongoing basis.

12.3 Protocol changes

Amendments to this trial protocol may be made following the procedures specified by local laws and regulations. Substantial amendments to this trial protocol may be implemented only if the approval of the CA(s) and a favorable opinion of the ethics committee(s) have been obtained.

Substantial amendments to the conduct of the clinical trial may arise from changes to the protocol or from new information relating to the scientific documents in support of the trial. Amendments to the trial are regarded as "substantial" where they are likely to have a significant impact on:

- the safety, physical health and mental integrity of the patients;
- the scientific value of the trial;
- the conduct or management of the trial; or
- the quality or safety of any investigational medicinal product used in the trial.

If a new event occurs related to the conduct of the trial or the development of the investigational product, which may affect the safety of the patients, the sponsor and the investigator will take appropriate safety measures to protect the patients against any immediate hazard. The sponsor will immediately inform the CA(s) and ethics committee(s) of the new events and the measures taken.

12.4 Publication of results

The original eCRFs and the data generated from the eCRFs or otherwise obtained during the trial under this trial protocol will become the property of the sponsor. Publication of the results of this trial by SynteractHCR or the investigator is possible only after written consent has been obtained from the sponsor. Any material intended for publication will be given to the sponsor at least 4 weeks before submission for publication. The sponsor will have the right to comment on the intended publication and to take any reasonable measures for patent protection.

12.5 Clinical trial report

After completion of the trial, the results will be tabulated, evaluated and issued as a complete final clinical trial report according to the ICH-E3 Note for guidance on structure and content of clinical trial reports.

The sponsor will send a summary of this clinical trial report to the EC and CA within one year after the end of the trial.

APPENDIX C: LIST OF TABLES, FIGURES, AND LISTINGS	51
LIST OF TABLES AND FIGURES FOR ANALYSIS	51
LIST OF DATA LISTINGS FOR ANALYSIS	57
APPENDIX D: TABLE LAYOUTS	59

LIST OF ABBREVIATIONS

ADA	Anti-drug antibody
AE	Adverse event
ATC	Anatomical therapeutic chemical
AUC _{0-30min}	Area under the plasma concentration curve from administration to observed concentration 30 min
AUC _{0-90 min}	Area under the plasma concentration curve from administration to observed concentration at 90 min
AUE _{0-30min}	Area under the effect curve from administration to 30 min
AUE _{0-90 min}	Area under the effect curve from administration to 90 min
CE _{max}	Change from baseline plasma glucose to maximum plasma glucose measured post dose
CFB	Change from baseline
CI	Confidence Interval
C _{max}	Maximum plasma concentration
CRF/eCRF	Case report form/electronic case report form
CSR	Clinical study report
e.g.	For example
ECG	Electrocardiogram
EoT	End of Trial
FAS	Full Analysis Set
ICH	International conference on harmonization
IMP	Investigational Medicinal Product
MedDRA	Medical Dictionary for regulatory activities
NAb	Neutralizing Antibody
PD	Pharmacodynamic(s)
PK	Pharmacokinetic(s)
PPS	Per protocol set
PT	Preferred term
SA (set)	Safety analysis (set)
SAE	Serious adverse event
SAP	Statistical analysis plan
SAS	Safety analysis set
SD	Standard deviation
SHCR	Contract research organization: SynteractHCR Deutschland GmbH, [name], 80636 Munich, Germany
SOC	System organ class

T1DM	Type 1 diabetes mellitus
T2DM	Type 2 diabetes mellitus
TEAE	Treatment-emergent adverse event
TLFs	Tables, listings, figures
t_{\max}	Time until C_{\max} is reached, time to maximum effect
ULN	Upper Limit of Normal
V	Visit
WHO	World Health Organization
WHO-DDE	WHO drug dictionary enhanced
ZP4207	dasiglucagon

DEFINITIONS

Treatment-emergent AE	AEs with an onset time at or after the initial dose of study drug.
End of trial	The trial ends with the last visit of the last patient participating in the trial.
Clinical (adverse) event of interest	
A clinical event of interest is an event which, in the evaluation of safety, has a special focus (e.g. required by health authorities). They will be recorded under the eCRF section adverse events.
 
In this trial hemodynamic changes, as defined below, are considered clinical events of interest:
 
• Post-dose clinical signs or measured vital signs indicating a clinical significant drop in blood pressure including signs of orthostatic hypotension, vasovagal responses or bradycardia.• Post-dose change in pulse or blood pressure considered an event of hypo- or hypertension as judged by the investigator.
ADA titer	A sample is defined as ADA-positive if results of the screening and confirmatory assays are positive. If positive, a titer (the reciprocal of the highest dilution factor that still yields a positive reading, e.g. dilution 1/10 = titer 10) will be reported. Any titer above zero defines positivity.
ADA-positive/ negative-subject (after baseline)	ADA-positive after baseline is a subject with at least one treatment-induced or treatment-boosted ADA positive sample at any time during the treatment or follow-up observation period. In contrast a ADA-negative subject after baseline is a subject without any treatment-induced or treatment-boosted ADA-positive sample at any time during treatment or follow-up.
Evaluable patients	A subject with at least one sample taken after drug

	
administration during the treatment or follow-up that is appropriate for ADA testing (with reportable result). This is the same definition as for the FAS population. Only evaluable subjects are considered for computing treatment-induced ADA incidence

Pre-existing/ baseline ADA	
Refers to antibodies reactive with the biologic drug that are present in subjects before treatment or before the initiation of the study.

Treatment-induced ADA	
ADA developed de novo (sero-conversion) following biologic drug administration (i.e., formation of ADA any time after the initial drug administration in a subject without pre-existing ADA).

Treatment-boosted ADA	
Pre-existing ADA that were boosted to a higher level following biologic drug administration (i.e., any time after the initial drug administration the ADA titer is greater than the baseline titer by a scientifically reasonable margin - in this study the fifth fold increase.

Overall ADA incidence	
Overall ADA incidence is defined as the percentage of the combined results of treatment-induced ADA-positive patients and treatment-boosted ADA-positive patients and the total number of evaluable patients, excluding baseline-positive patients without any samples available after drug administration.

Onset of ADA	
Refers to the time period between the initial administration of the biologic drug (in a study) and the first instance of treatment-induced ADA via blood sampling date. Elapsed days between the two dates will be used for calculation and not nominal study time points. Actual documentation of blood sampling date will be taken as reference.

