The results of the phase 1 and 2 clinical trials confirm dose-proportionality for dasiglucagon pharmacokinetics, which is characterized by a fast absorption with a peak plasma concentration obtained after 35 minutes. Thereafter, the plasma concentration rapidly declines with an average half-life of 28 minutes. The median time to the maximum plasma concentration (C_{max}) was later for dasiglucagon than for GlucaGen (35 versus 20 minutes). Doses of 0.3 mg dasiglucagon and 0.5 mg GlucaGen and also 0.6 mg dasiglucagon and 1.0 mg GlucaGen were similar with regard to C_{max} . For C_{max} , the results indicated that 0.3 mg dasiglucagon was comparable to 0.5 mg GlucaGen (90% confidence interval (CI): 0.8167; 1.0068) and 0.6 mg dasiglucagon was comparable to 1.0 mg GlucaGen (90% CI: 0.8850; 1.1991).³ At these dose levels, the total exposures (AUC_{0-inf}) were higher for dasiglucagon compared to GlucaGen.

At all dose levels in the phase 2 trial, all patients achieved a plasma glucose level of at least 70 mg/dL as well as an increase in plasma glucose by at least 20 mg/dL within 30 min post-dose. The maximal observed time to reach the 20 mg/dL plasma glucose increase ranged from 15 to 27 minutes across doses and decreased as the dose increased. The pharmacodynamic responses of 0.6 mg of dasiglucagon and 1.0 mg of GlucaGen were comparable.³

Safety of dasiglucagon

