- antiemetic treatment in the form of metoclopramide (Primperan[®]) as per local label, administered before or after dosing

At visit 3:

- patients will be allowed to eat and drink moderately to make them feel comfortable
- a moderate and individualized corrective dose of insulin to convert the induced hyperglycemia to euglycemia, after agreement with the investigator
- antiemetic treatment in the form of metoclopramide (Primperan[®]) as per local label, administered before or after dosing

Patients must be monitored for at least 5 h after dosing at the clinical site for safety observations, including blood glucose monitoring.

Patients will not be discharged until they are considered stable and with a blood glucose level in the range of 70-180 mg/dL. Before discharge, the investigator will provide instructions to the patients on management of their blood glucose levels. Each trial medication will be administered s.c. 3 times in total, with 7 days between dosing (i.e. dosing occurs at Days 0, 7, and 14; Visits 2, 3, and 4). Should the patient experience vomiting following the first or second dasiglucagon or GlucaGen administration, the investigator must ensure normal electrolytes prior to the next dosing day. An electrolyte imbalance can be corrected by administration of an electrolyte supplement or by any other treatment modality considered appropriate by the investigator.

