7.5.4 Follow-up period of the trial

After the final dose of trial medication (at Visit 4, Day 14, described above), patients will be followed up until Day 104 (Visit 7). During the follow-up period, visits take place at Days 35, 60, and 104 (Visits 5, 6, and 7).

At Visits 5 and 6 during the follow-up period, the following assessments will take place:

- Concomitant medication
- Check of withdrawal criteria
- AEs
- Antibodies against dasiglucagon/glucagon

Additionally, the following assessments will take place at Visit 5 only:

- Vital signs
- ECG
- Hematology and biochemistry

At Visit 7, the final visit of the follow-up period and of the trial (EoT visit), the following assessments will take place:

- Concomitant medication
- Physical examination
- Vital signs
- ECG
- AEs
- Hematology and biochemistry
- Urinalysis
- Antibodies against dasiglucagon/glucagon

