8.2 Collection, recording and reporting of adverse events

All events meeting the definition of an AE must be collected and reported from the first trial related activity after the patient has signed the informed consent until the end of the post-treatment follow-up period. At each contact with the site (visit or telephone, excluding visits, where the patient is not seeing the Investigator or his staff (e.g. visits to the laboratory)) the patient must be asked about AEs. All AEs, either observed by the Investigator or reported by the patient, must be recorded by the Investigator and evaluated.

The Investigator should record the diagnosis, if possible. If no diagnosis can be made the Investigator should record each sign and symptom as individual AEs.

All AEs must be recorded by the Investigator. One single Adverse Event Form must be used per AE from start to resolution. For SAEs, the Serious Adverse Event Form must also be completed. For clinical events of interest, the Clinical Event of Interest Form must also be completed.

AE information should include the following:

- Date and time of onset and resolution
- Date and time of Investigator's first information on the (S)AE
- Seriousness
- Severity
- Causal relationship with IMP
- Interruption or withdrawal of treatment with IMP and other measures taken
- Outcome

All AEs are coded; details are described in the trial specific Data Management Plan.

If an event classifies as a clinical event of interest, the Investigator must tick the Clinical Event of Interest box on the AE form and complete the Clinical Event of Interest Form. The Clinical Event of Interest form will capture if the event was associated with any signs or symptoms and capture the highest/lowest blood pressure and pulse measured during the event.

The Investigator must report initial information in writing (fax or email) on all SAEs to the Sponsor's responsible pharmacovigilance unit (Safety CRO) immediately (within 24 hours) after

obtaining knowledge about the event. Please refer to Appendix 1 for contact details. The Safety CRO will inform the medical monitor and the sponsor about the reported SAEs.

It is the responsibility of the Safety CRO to report all SUSARs that occur in this trial to the Competent Authorities and IRBs/IECs in accordance with the local requirements in force and ICH guideline for GCP. The trial monitor must be informed accordingly.

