8.4 Hypoglycemia

Hypoglycemia will be regarded as an AE and recorded and documented on an AE Form.

Hypoglycemia is defined as a fall of plasma glucose below 3.9 mmol/L (70 mg/dL).

During the dosing visits, mild to moderate symptoms of hypoglycemia, or a blood glucose (BG) value less than a threshold of <2.8 mmol/L (50 mg/dL), corresponding to a plasma glucose (PG) value of <3.1 mmol/L (56 mg/dL), will be treated by i.v. glucose solution at the investigator's discretion according to best available medical practice. Treatment is to be repeated until BG value stabilized above the threshold limit again. BG measurements will only be done due to safety concerns. Insulin-induced hypoglycemia should be recorded as an AE.

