- If the onset date of the AE is at the same day or after the start of the IMP drug administration date, then the AE is classified to the treatment period and is therefore treatment-emergent. For the adverse events accounting to the screening phase the start date of the adverse event may not be later than the start date of the interventional phase (= date of first administration of the IMP).
- If any date part is missing, the procedures for imputing missing date parts should be applied first.

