14.1.3 Adverse event tables

In addition, frequency tables will be prepared stratified by MedDRA terms (SOC, PT) showing the following:

1. All TEAEs
2. All clinical events of interest
3. All injection site reactions
4. Study-drug related TEAEs (ADRs)
5. TEAEs by causal relationship to study drug
6. TEAEs by intensity grading
7. Serious TEAEs (SAEs)

The analysis of AEs will include summary tables displaying counts and percentages of subjects experiencing adverse events by system organ class and preferred term. If a subject has more than one AE which codes to the same preferred term, the subject will be counted only once for that preferred term. The total number of events documented per system order class (SOC) and preferred team (PT) will also be displayed.

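### With an open-ended TEAE window and AE tables split by arm only, the overall TEAE row and the hypoglycemia rows mix acute post-dose events with background events up to Day 104

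*SAP*

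**What the plan says.** The SAP Definitions describe treatment-emergent AEs as "AEs with an onset time at or after the initial dose of study drug". SAP 14.1.1 gives the working rule on the calendar date instead: "If the onset date of the AE is at the same day or after the start of the IMP drug administration date", the event belongs to the treatment period. Neither rule has an upper limit. Protocol 8.2 collects AEs "until the end of the post-treatment follow-up period", and Protocol 7.5.4 places the last visit at Day 104. Dosing is on Days 0, 7 and 14.

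Protocol 8.4 states "Hypoglycemia is defined as a fall of plasma glucose below 3.9 mmol/L (70 mg/dL") and requires hypoglycemia to be recorded as an AE, with no symptom or severity condition.

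SAP 14.1.1 presents all AE tabulations by treatment group. The overview (14.1.2) and the SOC and preferred-term tables (14.1.3) add no split by dose number, visit or time since dose. Within a preferred term "the subject will be counted only once for that preferred term"; the number of events is shown as well. The exception on timing is SAP 14.1.5, which tabulates injection site reactions at 0.5 h and 2 h for each visit.

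The secondary objective (Protocol section 6) covers safety and tolerability of repeated single doses compared with GlucaGen.

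**The concern.** Dasiglucagon leaves the body quickly: "the plasma concentration rapidly declines with an average half-life of 28 minutes" (Protocol 5.1). Acute effects should therefore cluster in the hours after each injection. The planned tables pool those hours with about 90 days of ordinary insulin-treated life after the last scheduled dose, during which any recorded glucose below 70 mg/dL adds a TEAE. If background events are common and similar in both arms, they bring the arms together in any row that includes hypoglycemia.

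The pooled tables also cannot show whether reactions change from dose 1 to dose 3, which is a natural question for repeated dosing in an immunogenicity trial. Nor do they separate events after the extra dose that ADA-positive patients receive under Protocol 7.5.6. Vital signs and ECG, by contrast, are summarized by visit and time point (SAP 14.3.1, 14.4).

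**Working it through.** The documents give no figure for the AE burden, so there is none to reproduce.

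**Window.** From dose 1 to Day 104 is 104 × 24 = 2,496 h. Three 24-h post-dose periods are 72 h, and 72/2,496 = 2.9%. The time after the last scheduled dose is (104 − 14)/104 = 87%. At the end of the 5-h observation period, 300/28 = 10.7 half-lives have passed and 0.5^10.7 = 0.06% of the drug remains.

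**Rates.** The only background rate in the documents is 0.21 to 1.6 episodes per patient-year (Protocol 5.1). It refers to rescue use, so it does not cover milder readings below 70 mg/dL. The recorded rate of such readings is not given; 0.05, 0.1 and 0.5 per patient-week are assumptions.

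**Formulas.** With a constant rate r, equal in both arms, the share of patients with at least one background event in time t is b = 1 − exp(−r·t). If acute AEs occur in proportions p1 and p2, independently of background, the any-TEAE proportion in an arm is 1 − (1 − p)(1 − b). The difference between arms is then (p1 − p2)(1 − b). The illustration assumes 65% v 50%, a 15-point acute difference.

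| Background rate | Source | b over 104 days | Difference, full window | b over 3 × 24 h | Difference, 24-h windows |
|---|---|---|---|---|---|
| 0.21 per year | Protocol 5.1 | 5.8% | 14.1 points | 0.2% | 15.0 points |
| 1.6 per year | Protocol 5.1 | 36.6% | 9.5 points | 1.3% | 14.8 points |
| 0.05 per week | assumed | 52.4% | 7.1 points | 2.1% | 14.7 points |
| 0.1 per week | assumed | 77.4% | 3.4 points | 4.2% | 14.4 points |
| 0.5 per week | assumed | 99.9% | below 0.1 points | 19.3% | 12.1 points |

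Examples: 1.6 × 104/365.25 = 0.456 and 1 − exp(−0.456) = 0.366, so 15 × 0.634 = 9.5. At 0.05 per week, 0.05 × 104/7 = 0.743 and 1 − exp(−0.743) = 0.524, so 15 × 0.476 = 7.1.

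**Event totals.** The expected background count per patient over 104 days is 0.06 to 0.46 at the documented rates and 0.74 to 7.43 at the assumed ones. At a constant rate, 100% − 2.9% = 97.1% of these events fall outside the three 24-h periods.

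**Rows affected.** The calculation applies to the any-TEAE row and, in the same way, to the SOC that contains hypoglycemia. The hypoglycemia row itself cannot separate an event hours after dosing from one late in follow-up. A nausea or vomiting row contains no hypoglycemia events, so this mechanism leaves it unchanged.

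**Onset time against onset date.** Protocol 7.4.2 foresees patients arriving with glucose below 70 mg/dL before dosing. On Day 0 such an event is not treatment-emergent under the SAP Definitions (onset time) but is under SAP 14.1.1 (onset date).

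**The case against.** The long window is deliberate. Protocol 7.2 expects immune responses to be most pronounced around Day 35 and follows patients to Day 104 for that reason. Protocol 5.3 says that antibodies could in theory reduce endogenous glucagon activity and so influence hypoglycemic episodes. Late hypoglycemia may thus be a consequence of ADA, and a 28-minute plasma half-life says nothing about delayed immune effects. This stands: the open-ended definition is not an error, and tables limited to 24 h should not become the only tolerability comparison.

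A reader might infer that background hypoglycemia overwhelms the whole tolerability comparison. The documents do not support that. SAP 14.1.3 gives nausea, vomiting and headache their own rows and plans tables of drug-related TEAEs, TEAEs by relationship, clinical events of interest and injection site reactions. The denominators are patients, so the 2.9% share of time does not by itself dilute an incidence. A reader might also infer that no AE is shown by dose; SAP 14.1.5 shows injection site reactions per dosing visit.

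The assumed weekly rates may be too high. No glucose diary is described, and AEs outside the clinic are elicited by asking at contacts. All analyses are descriptive, and onset times would allow a later summary. These points limit the consequence. They do not supply the missing tables, and an analysis added after database lock would be post hoc by the SAP's own rule (section 6).

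Metoclopramide may be "administered before or after dosing" (Protocol 7.4.2), which might suggest splitting nausea by antiemetic use. That is a separate, debatable matter and is not part of this point.

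**Conclusion.** The point holds for four displays: the any-TEAE row, the total event counts, the SOC containing hypoglycemia and the hypoglycemia row. In these, acute and background events cannot be told apart, and outside injection site reactions no AE table shows dose number or time since dose.

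The size is uncertain. On the documented rescue-episode rate, 6% to 37% of patients would enter the any-TEAE row through background alone, and an acute difference in that row would lose the same share. Heavier loss rests on assumed recorded rates. All figures assume a constant rate, equal arms and independence from acute events. The mismatch between onset time and onset date is a separate small inconsistency that needs no assumption.

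This is an inexpensive reporting improvement, not a flaw that invalidates the safety analysis.

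**What to change.** Keep the TEAE flag and all full-window tables. Add to SAP 14.1.2 and 14.1.3:

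- TEAEs with onset within a prespecified window, for example 24 h, after dose 1, dose 2 and dose 3, by arm;
- TEAEs with later onset;
- TEAEs after an unscheduled ADA-visit dose, shown separately;
- the any-TEAE row with and without hypoglycemia.

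Assign events to these windows by onset time, so that a pre-dose event on a dosing day is not counted as following that day's dose. State how a dosing-day event without an onset time is handled. Reconcile the SAP Definitions (onset time) with SAP 14.1.1 (onset date).

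The cost is a few descriptive tables and a conventional choice of window. Protocol 8.2 already collects the date and time of AE onset, so no new data are needed.
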